13.2 Study Endpoints

13.2.1 Primary Endpoint

The primary endpoint will be the incidence for any of the following complications from surgery within 24 weeks after surgery: 30-day mortality, 30-day re-hospitalization, pulmonary complications, ICU readmission (an upgrade from any inpatient status [floor or intermediate care status] to full intensive care nursing acuity because of a serious deterioration in physical condition that warrants closer physician monitoring or nursing care), wound infection (NOS), anastomotic failure. These complications were identified as being sufficiently numerous from an investigation of the national surgical database (ACS-NSQIP). They will be defined using the General Thoracic Surgery Database (GTSD) for study purposes. These complications will be considered equally important in determining complication rates. Patients who have any of these individual morbidities will be considered to have a perioperative complication. Patients without any of these individual morbidities will be considered to not have a perioperative complication.

Formal definitions for all complications of the primary and secondary endpoints are found in Appendix X. We have reviewed the elements of the primary endpoint with the Community Oncology Committee and the Alliance lung cancer surgeon working group and surveyed potential participating sites for a description of the workflow for treatment administration and data collection to ensure that all the elements can be recorded across the Alliance sites.

13.2.2 Secondary Endpoints

- QOL-related domains as measured by the LASA-12, PHQ-9, SEQ-12, and Was It Worth It assessments.
- Post-operative care as measured by length of hospital and high dependency unit stay. Length of stay will include only the time from surgery until the patient is released from the hospital.

- Expanded complication rate defined as any of the complications listed in Appendix I that are not being examined as part of the primary endpoint. This is included to account for the possibility that other complications, which do not occur with high frequency in the ACS-NSQIP data base, actually occur in our study.
- Treatment adherence rates related to visits, medication compliance, quitline usage, and surgeon teachable moment delivery.
- Smoking abstinence rates as measured by self-report and salivary cotinine testing.

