13.4 Additional Analyses

We will compare changes from baseline in patient quality of life related domains (LASA-12, PHQ-9, SEQ12) between the intervention and control groups using analysis of covariance and linear mixed model repeated measures analysis for each assessment domain. Specifically, we will analyze each LASA domain with a separate ANCOVA model using the change from baseline to 12 weeks post-surgery as the dependent variable, followed by a similar analysis using the change from baseline to 24 weeks post-surgery. Each LASA question corresponds to a separate domain. For the PHQ-9 and SEQ12, we will use the scale scores in a repeated measures analysis involving data from all time points (baseline, 6, 12, and 24 weeks). For the PHQ-9 there is one overall score and for the SEQ12 there are two scales (internal stimuli and external stimuli).

The WIWI survey will be analyzed by comparing the proportion of patients at the end of the treatment period (i.e., 12 weeks after surgery) and at 24 weeks after surgery who endorse each treatment (intervention versus control) via Fisher's exact testing.

These QOL-related domain variables will be included in the modeling process of the primary and other secondary analyses as potentially concomitant confounding covariates so as to produce more efficient estimates from the models. Sensitivity analysis for potential differences between groups demonstrated via the ANCOVA and repeated measures models will be assessed using Generalized Estimating Equations models to account for the correlation of repeated measures on the same patient.

We will compare post-operative care (length of hospital and high dependency unit stay) between the intervention vs. control groups using separate logrank testing of Kaplan-Meier estimates for length of hospital stay and length of high dependency unit stay and supplemented by Cox models to control for concomitant covariates. The assumptions underlying the Cox model will be tested for veracity.

For the expanded complication rate, we will utilize the same analysis approach as the primary endpoint analysis for all complications listed in Appendix I. We will also compare the incidence rates of each specific type of complication between arms.

We will also measure treatment adherence. The number of study visits completed by each patient during the treatment phase will be summarized and compared between groups using the rank

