APPENDIX I: SURGICAL COMPLICATIONS ASSOCIATED WITH CIGARETTE SMOKING [104]

30-day mortality 30-day re-hospitalization 1-year mortality Anastomotic failure Anesthesia-related respiratory complications Bleeding (transfusions >5 U) Coma (>24 hours) Deep venous thrombosis/thrombophlebitis Failure to wean from the ventilator ICU readmission Impaired bone healing Implant loss (breast reconstruction)	Increased postoperative pain Renal insufficiency/failure Return to operating room Sepsis/septic shock Stroke/cerebral accident Surgical infection (organ space) Surgical site infections Urinary tract infections Increased postoperative surgical stay Increased scarring and asymmetry Intubation (unplanned)/re-intubation Lower rates of successful digital replantation (microsurgery) Myocardial infarction	Pneumonia Prolonged intubation Prolonged ventilator support Pulmonary complications Pulmonary embolism Reduced skin flap survival Vascular complications Vein graft failure Venous thromboembolism Ventilator (>48 hours) Wound healing (delayed) Wound infection (sternal) Wound infections (superficial and deep)
--	---	---

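### The expanded complication rate excludes the primary components in section 13.2.2 but includes them in section 13.4, so the 13.4 version can be significant through primary events alone

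*Combined protocol and SAP*

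**What the plan says.** The primary endpoint (section 13.2.1) is any of six complications "within 24 weeks after surgery: 30-day mortality, 30-day re-hospitalization, pulmonary complications, ICU readmission", wound infection not otherwise specified, and anastomotic failure.

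Section 13.2.2 adds a secondary endpoint: "Expanded complication rate defined as any of the complications listed in Appendix I that are not being examined as part of the primary endpoint". Its stated purpose is to allow for the possibility that "other complications, which do not occur with high frequency in the ACS-NSQIP data base, actually occur in our study".

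Section 13.4 says how it will be analysed: "For the expanded complication rate, we will utilize the same analysis approach as the primary endpoint analysis for all complications listed in Appendix I". The next sentence adds that each specific type of complication will also be compared between arms.

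Appendix I, repeated in section 9.1, is a general list of surgical complications associated with smoking. It names 30-day mortality, 30-day re-hospitalization, pulmonary complications, ICU readmission and anastomotic failure, and has two wound-infection items. It also contains "Increased postoperative pain", "Increased postoperative surgical stay", an item on greater scarring and asymmetry, an item on success rates of digital replantation, breast implant loss and 1-year mortality.

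Section 9.1 has the list collected at 24 weeks after surgery. The intent-to-treat definition in section 13.1.1 counts patients with missing values as having complications. Section 13.2.1 refers to Appendix X for formal definitions, but Appendix X is the adherence log; the surgical definitions are in Appendix XI.

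**The concern.** The two sections give one endpoint two event sets, one without the primary components and one with them. A programmer working from 13.2.2 and a programmer working from 13.4 would derive different variables. Under 13.4 every patient with one of the named primary components is also an expanded-rate event, so the result partly repeats the primary one. That defeats the purpose given in 13.2.2, which is to learn about other complications. While the choice is open, it could also be made after the results are known.

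A second difficulty concerns what can be scored. The pain, stay and scarring items are comparatives with no reference value or threshold in the documents, and Appendix XI defines none of them. The digital replantation item is worded as a rate in a group, not an event in a patient. One-year mortality cannot be fully observed at 24 weeks. Because 13.4 borrows the primary approach, the missing-equals-complication rule, read literally, could turn an unobservable item or a blank not-applicable item into an event.

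**Working it through.** **The plan's own figure.** Section 13.6 gives 313 per arm for 20% versus 30%, two-sided 5%, 80% power, Fisher's exact test.

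- Without continuity correction: n = [1.960·√(2·0.25·0.75) + 0.842·√(0.20·0.80 + 0.30·0.70)]² / 0.10² = 293.2, so 294.
- With continuity correction: n′ = (n/4)·[1 + √(1 + 4/(n·0.10))]² = 312.8, so 313.
- Exact enumeration of the two-sided Fisher test at 313 per arm gives power 0.802.
- Enrolment: 626 / (1 − 0.20) = 782.5, so 783.

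The stated figures reproduce. They belong to the primary endpoint; the documents give no rate, effect or power for the expanded rate.

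**Size of the two event sets.** Appendix I has 12 + 13 + 13 = 38 items, all of which count under 13.4. Under 13.2.2, removing the five primary components listed by name leaves 33. Treating the sternal and the superficial/deep wound infection items as the primary wound-infection component leaves 31. The boundary is not settled: pneumonia, re-intubation and prolonged ventilation could already count as pulmonary complications, and the surgical site items could count as wound infection.

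**What the choice does to the result.** Inputs: 313 per arm and primary rates of 20% (varenicline) and 30% (placebo) from section 13.6. Assumed: a rate q of other Appendix I events, equal in both arms and independent of the primary events.

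- Exclusive rate (13.2.2) = q in each arm.
- Inclusive rate (13.4) = 1 − (1 − p)(1 − q), where p is the primary rate.

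For q = 0.15:

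- Varenicline: 1 − 0.80·0.85 = 0.320; 0.320·313 ≈ 100 patients.
- Placebo: 1 − 0.70·0.85 = 0.405; 0.405·313 ≈ 127 patients.
- Fisher's exact test on 100/313 versus 127/313: p = 0.031. The exclusive rate is 15% in both arms.

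Probability of a two-sided Fisher p-value of at most 0.05, by exact enumeration:

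| Assumed q, both arms | Exclusive rates | Exclusive rejects | Inclusive rates (placebo vs varenicline) | Inclusive rejects |
|---|---|---|---|---|
| 5% | 5% vs 5% | 3.2% | 33.5% vs 24.0% | 72% |
| 10% | 10% vs 10% | 3.6% | 37.0% vs 28.0% | 64% |
| 15% | 15% vs 15% | 3.8% | 40.5% vs 32.0% | 57% |
| 20% | 20% vs 20% | 3.9% | 44.0% vs 36.0% | 50% |

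No row contains a treatment effect on non-primary events. All of the inclusive version's rejection above the nominal level comes from the primary components.

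**The case against.** The strongest defence is that 13.2.2 is the definition and 13.4 only describes a method, so its reference to all of Appendix I is shorthand. That reading is possible. But 13.4 is the analysis text, its words are explicit, and nothing in it limits the list to non-primary items.

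It is also fair that this is a supportive endpoint. It appears in none of the secondary objectives in section 2.2 and has no stated power or alpha. That limits the importance of the point but does not remove the conflict.

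Four stronger readings might be inferred, and the documents do not support them.

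- *The definitions are opposite and give opposite conclusions.* They are exclusive versus inclusive and share 31 to 33 of 38 items. The illustration sets no difference against a benefit, not benefit against harm.
- *A noisy composite would hide differences in stroke, sepsis or myocardial infarction.* Section 13.4 also compares each specific type of complication between arms, so those events are examined individually under either definition.
- *Loosely ticked pain or stay items would push both arms towards 100%.* This is conjecture. The case report forms are not among the documents, so it is unknown whether they set thresholds or how sites would complete them.
- *Breast implant loss and digital replantation add noise.* In lung-surgery patients they would be recorded as absent and add nothing to an any-event composite. More broadly, most Appendix I items are ordinary patient-level events, and Appendix XI defines several of them, including myocardial infarction, pulmonary embolism and renal failure.

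**Conclusion.** The conflict is real and should be resolved before analysis. Followed as written, 13.4 produces a composite that can be significant purely through the primary components: about 57% of the time, against about 4% for the 13.2.2 version. This assumes a 15% rate of other events in both arms, independence from the primary events, and the planned 20% versus 30% primary rates. Over assumed rates from 5% to 20% the contrast runs from 72% against 3% to 50% against 4%. If the primary effect is smaller than planned, the contrast shrinks.

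The scoring problem is narrower. It concerns three comparative items with no printed threshold, one group-rate item, 1-year mortality, and an unstated limit on the missing-data rule. The size of its effect cannot be derived from the documents.

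The primary endpoint, its test and the sample size are unaffected.

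**What to change.** 1. In section 13.4, restrict the expanded rate to Appendix I complications that are not components of the primary endpoint, matching 13.2.2.
2. State which pulmonary items (such as pneumonia, re-intubation and prolonged ventilation) and which wound or surgical-site items already count as primary components.
3. If a composite of all Appendix I events is wanted, report it separately under its own name and say that it contains the primary events.
4. Leave out of the composite increased postoperative pain, increased postoperative surgical stay, increased scarring and asymmetry, the digital replantation item and 1-year mortality. Removing breast implant loss is only tidying. Length of stay keeps its own secondary endpoint. The pain items of the LASA (12 and 24 weeks, past-week recall) do not replace a measure of early postoperative pain.
5. State that the missing-equals-complication rule does not apply to not-applicable or unobservable items.
6. Correct the appendix reference in section 13.2.1.

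The cost is SAP wording and a shorter derivation list, with no new data. The downside is a lower expanded rate. The comparisons of individual complications in 13.4 stay as they are.

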13.3 Primary analysis

Surgical complication incidence rates at 24 weeks after surgery will be compared between the intervention vs. control groups using a Fisher's exact test.

Logistic regression models will supplement the univariate analysis, using complication incidence as the dependent variable and will include smoking status at the time of surgery as an independent variable and also adjust for age, gender, FTND, time between randomization and surgery, and presence of adjuvant chemotherapy and/or radiation therapy. A separate logistic model will be created including treatment arm instead of smoking status. We will also explore the collinear relationship between arm and smoking status to see whether they can be included together in the logistic models.

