13.6 Power/Sample Size

The primary statistical endpoint for this study is the incidence of surgical complications as described in Sections 13.1 and 13.3. Patients that have any of these individual morbidities will be considered to have a perioperative complication. Patients without any of these individual morbidities will be considered to not have a perioperative complication.

In a study of 635,265 non-cardiac surgical cases treated in 200 centers throughout the United States, the incidence rate of the perioperative complications listed above from the National Surgical Quality Improvement Program (NSQIP) data was in the range of 25–30%. They further found that smokers undergoing non-cardiac surgery had an estimated 40% increased odds of developing major morbidity and mortality within 30 days of surgery over never smokers, representing a modest difference of between 10%-12% in the actual percentage of patients with major morbidity.[90] One report focused on the limitations of NSQIP in identifying adverse events following major cancer surgery. NSQIP does not abstract the complications considered most important by many surgical subspecialists (e.g., anastomotic leak).[91] Therefore, the true impact of smoking on adverse surgical events may be greater in this trial.

For the purposes of this power calculation then, we will assume a 30% perioperative complication incidence rate in the control group.¹⁰⁴ The study design is a randomized clinical trial intended to estimate the incidence rate of perioperative complications in patients who are smoking at the time of enrollment. The primary statistical analysis will be a comparison of the perioperative complication incidence rates from the time of surgery to 24 weeks after surgery between the intervention and control groups. We will hence power the study to detect a 10% difference in perioperative complication rates between the intervention and control groups.

With a sample size of 626 patients (313 patients per arm), a Fisher exact test can detect a difference in the perioperative complication rate between the two treatment groups of 10% (20% versus 30% in the intervention arm and control arm, respectively) with 80% power using a Type I error rate of 5% and a two-sided alternative.

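### The primary Fisher exact test is valid and delivers the planned power, but it is conservative and leaves baseline covariates unused: a modest, inexpensive gain in efficiency is available

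*Combined protocol and SAP*

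**What the plan says.** Section 13.3 makes the primary comparison unadjusted: "Surgical complication incidence rates at 24 weeks after surgery will be compared between the intervention vs. control groups", with Fisher's exact test as the method. Regression comes second: "Logistic regression models will supplement the univariate analysis". The first such model has smoking status at surgery as its main term and will "also adjust for age, gender, FTND, time between randomization and surgery, and presence of adjuvant chemotherapy and/or radiation therapy". The arm effect enters only in a further model: "A separate logistic model will be created including treatment arm instead of smoking status".

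Section 13.6 sizes the trial on the same test. With 313 per arm, "a Fisher exact test can detect a difference in the perioperative complication rate between the two treatment groups of 10" percentage points (20% against 30%) with 80% power, "using a Type I error rate of 5% and a two-sided alternative".

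Two other sections bear on the point. Section 13.4 brings quality-of-life variables into the modelling to gain efficiency, again outside the primary test. Section 13.10 sets a P-value bound of 0.001 for interim looks tied to the semi-annual DSMB reports and keeps 5% for the final analysis.

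**The concern.** Fisher's test conditions on the total number of events. Because that makes the reference distribution discrete, the test rejects less often than its nominal level allows. It earns its place when cell counts are small. Here the smallest expected count is 313 × 0.20 = 62.6, so counts give no reason to accept the conservatism.

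Age, gender and FTND are also recorded for every patient and already named as adjusters, yet the primary test does not use them. The only planned adjusted arm model is supplementary. It also carries time from randomization to surgery and adjuvant therapy, both of which arise after randomization, so it could not simply be promoted to primary as it stands.

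At stake are a few points of power in a trial planned at 80%, and an adjusted effect estimate on the scale on which the trial was powered. Section 13.3 names a test but no effect estimate or confidence interval for the primary comparison.

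**Working it through.** **Inputs.** 313 per arm, 20% against 30%, two-sided 5%, 80% power (Section 13.6); interim bound 0.001, final level 5% (Section 13.10). The prognostic strength of the covariates is not given and is treated as an assumption.

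**1. Reproduce the plan's figure.** Pooled formula with mean rate 0.25:

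n = [1.960 × √(2 × 0.25 × 0.75) + 0.842 × √(0.30 × 0.70 + 0.20 × 0.80)]² / 0.10² = (1.200 + 0.512)² / 0.01 ≈ 293.2, so 294 per arm.

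Continuity correction, which approximates Fisher's test:

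n′ = (293.2 / 4) × [1 + √(1 + 4 / (293.2 × 0.10))]² ≈ 312.8, so 313 per arm.

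This matches the plan exactly.

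**2. Exact behaviour at 313 per arm.** All 314 × 314 possible tables were enumerated. Power is the binomial probability of rejection at 20% and 30%. Size is the same probability with one common rate in both arms.

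| Test | Power | Size |
|---|---|---|
| Fisher | 80.2% | 3.8% to 4.1% (common rates 15% to 40%) |
| Mid-P | 82.5% | 4.9% to 5.0% (15% to 35%) |
| Pearson chi-square | 82.7% | 4.98% to 5.05% (15% to 40%) |
| Boschloo | about 81% | held at 5% |

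Chi-square gains 82.7 − 80.2 = 2.5 points. Boschloo's test, which keeps a strict 5%, gains about 1. As a measure of the same loss, chi-square reaches 80% power at about 292 per arm.

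**3. Covariate adjustment.** Approximate the gain by an effective sample size of 313 / (1 − R²) in the unadjusted power formula:

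| Assumed R² | Power | Gain over R² = 0 |
|---|---|---|
| 0 | 82.5% | 0 |
| 0.02 | 83.3% | 0.8 points |
| 0.05 | 84.4% | 1.9 points |

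A simulation of a logistic likelihood-ratio test (4,000 replicates, five covariates, marginal rates held at 20% and 30%) agrees. Adjusted power was 82.7% at R² = 0, 83.0% at 0.018 and 84.8% at 0.048, against 83.1%, 82.6% and 83.3% for chi-square on the same data. The simulation standard error is about √(0.83 × 0.17 / 4000) = 0.6 points.

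**4. Interim looks.** Overall type I error was simulated with equally spaced looks (assumption), bound 0.001 at each and nominal 5% at the end, common rates 25% and 30%, 1,000,000 replicates. Accrual of about 50 months with semi-annual reports suggests up to about 8 looks.

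| Interim looks | Chi-square at the end | Fisher at the end |
|---|---|---|
| 3 | 5.1% | 4.1% to 4.2% |
| 8 | 5.2% | 4.2% to 4.3% |

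**The case against.** The planned test and the sizing test are the same, so nothing in the plan is inconsistent. A reader might infer from the 4% that the stated 5% type I error is wrong. It is not: 5% is the nominal level, and a valid exact test stays at or below it. A reader might also infer that the trial is underpowered or its sample size miscalculated. Step 1 reproduces 313 and step 2 gives 80.2%, so the documents support neither reading.

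The gain is small, and its covariate part cannot be established from the documents. No section says how strongly age, gender or FTND predict surgical complications. A figure such as 84% power is therefore conditional, and most of the distance to it comes from replacing Fisher's test, not from adjustment. An adjusted arm model is already planned in a supporting role.

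Fisher's conservatism also has a use: it absorbs the type I error that the interim looks add and that the full 5% final level does not pay for. Without that slack, overall error rises to about 5.1% to 5.2%.

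All of this stands, and it sets the weight of the point. It does not remove it. The unadjusted gain is certain under the plan's own rates, the interim excess is small and can be declared, and the planned adjusted model contains variables that should not enter a primary treatment comparison.

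**Conclusion.** The primary analysis is valid and meets its stated power. It is modestly inefficient. The part that rests only on the plan's own inputs is about 2.5 points of power with chi-square, or about 1 point with Boschloo's test. Adjustment for age, gender and FTND adds about 0 to 2 points if they explain 0 to 5% of outcome variance, and close to nothing if they are weak predictors. The interim figures depend on the assumed number and spacing of looks. The change is worth making because it uses data already collected and needs no more patients, not because the present plan is wrong.

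**What to change.** Before unblinding:

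- **Section 13.3.** Make the primary analysis the arm effect from a logistic model with arm, age, gender and FTND only. Report it as a standardised risk difference with 95% CI, and name in advance the test that decides significance.
- **Variables to leave out of that model.** Smoking status at surgery, time to surgery and adjuvant therapy, because they arise after randomization. They can stay in the exploratory models.
- **Missing baseline covariates.** Fill them by a simple prespecified rule that does not depend on arm, such as the overall mean or most frequent category. FTND is the likely gap: the study calendar in Section 5.0 places it at a visit held after randomization. Section 7.3 supplies drug only after that visit, so treatment should not have affected it.
- **Sensitivity analysis.** Keep Fisher's test. If the sponsor prefers an unadjusted primary test, chi-square or Boschloo's test would recover part of the loss.
- **Section 13.6.** Keep 626 patients and update the test named there; 626 remains sufficient.
- **Section 13.10.** State which test the interim looks use. Note that without Fisher's slack overall type I error may slightly exceed 5%, and either accept this openly or lower the final level a little.

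The cost is wording in three sections. No new data, visits or patients are needed.
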